	Day -28 to First Treatment	V1	V2	V3	V4	V5	V6	V7				
	W1	W3	W5	W7	W9	W11	W13	Until PD				
	D1	D15	D29	D43	D57	D71	D85					

Patient Reported Outcomes (PRO)

Assessments & Procedures	Screen-ing/ Base-line	Treatment Phase ( $\pm$ 3 days)							End-of-Treatment Visit	Safety Follow-up Visit		Long-term Follow-up	Notes				
	Day -28 to First Treatment	V1	V2	V3	V4	V5	V6	V7	Until PD	On the Day of or Within 7 Days of Decision to Discontinue	28 Days ( $\pm$ 5 Days) After Last Treatment	12 Weeks ( $\pm$ 2 Weeks) After Last Treatment	Every 12 Weeks ( $\pm$ 2 Weeks)				
		W1	W3	W5	W7	W9	W11	W13			D1	D15	D29	D43	D57	D71	D85
Patient interviews	X									X							Participants will be asked to participate in an interview performed by a third-party vendor. Participants will be selected from all sites in the USA, Germany, and Korea.
Tumor Assessments																	
Tumor evaluation /staging (CT scan/MRI/other established methods)	X					X			Q8W up to 12 months, then Q12W				X m	A brain CT/MRI scan should be done as clinically indicated at Screening. Confirmation of CR or PR should be performed preferably at the regularly scheduled assessment intervals, but no sooner than 4 weeks after the initial documentation. See Section 8.1.1. The IRC should confirm measurable disease before enrollment as well as verify unconfirmed PD by Investigator read.	m In case treatment is discontinued due to another reason than PD, tumor assessments should be continued according to original protocol schedule until confirmed PD.		
Subsequent anticancer therapy (any line)										X	X	X					
Survival follow-up n													X n	n Survival Follow-up will continue until each participant was followed up for at least 3 years after the End-of-Treatment.			

Assessments & Procedures	Screen -ing/ Base-line	Treatment Phase (± 3 days)							End-of-Treatment Visit	Safety Follow-up Visit		Long-term Follow-up	Notes			
	Day -28 to First Treatment	V1	V2	V3	V4	V5	V6	V7	Until PD	On the Day of or Within 7 Days of Decision to Discontinue	28 Days (± 5 Days) After Last Treatment	12 Weeks (± 2 Weeks) After Last Treatment	Every 12 Weeks (± 2 Weeks)			
		W1	W3	W5	W7	W9	W11	W13			D1	D15	D29	D43	D57	D71
PK, ADA and CCI																
PK and ADA sampling	See Table 2 for PK and ADA sampling times															

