#### 9.4.1.2                   Analysis of Secondary and CCI Endpoints

##### 9.4.1.2.1               Analysis of Secondary Endpoints

PFS according to RECIST 1.1, is defined as the time from first administration of study intervention until date of the first documentation of PD or death due to any cause in the absence of documented PD, whichever occurs first.

PFS data will be censored on the date of the last adequate tumor assessment for participants who do not have an event (PD or death), for participants who start new anticancer treatment prior to an event, or for participants with an event after two or more missing tumor assessments. Participants who do not have a baseline tumor assessment or who do not have any postbaseline tumor assessments will be censored on the date of first administration of study intervention unless death occurred on or before the time of the second planned tumor assessment, in which case the death will be considered an event.

Sensitivity analyses of PFS will be done including but not limited to:

- Alternative censoring rules including an analysis which counts death and progression according to RECIST 1.1 as PFS event regardless of the start of a new anticancer therapy and ignoring the number of missing evaluable tumor assessments before progression or death
- PFS as assessed by the Investigator

Details will be defined in the IAP.

DOR is defined, for participants with a confirmed OR, as the time from first documentation of OR (CR or PR) to the date of first documentation of objective PD or death due to any cause whichever occurs first. The censoring rules for DOR are as described above for PFS.

A durable response is defined as an OR (CR or PR) according to RECIST 1.1, determined by an IRC, with a duration of at least 6 months. Participants for whom the DOR is censored will be treated as failures (successes) in the analysis of durable response if the censored DOR is below (at least) 6 months. The DRR is defined as the percentage of participants with durable response. The 95% CI for the DRR will be calculated using the Clopper-Pearson method.

Overall survival (OS) is defined as the time from first administration of study intervention to the date of death due to any cause. Participants last known to be alive will be censored at date of last contact.

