## 14.4

## Progression-Free Survival (Secondary Endpoint)

Analysis (Analysis Population)	Derivation	Statistical Analysis Methods	Missing data handling
Secondary endpoint: Progression-Free Survival (PFS)			
Secondary analysis (ITT)	Time from first administration of study treatment until the first documentation of progression of disease (PD) or death due to any cause, whichever occur first, per RECIST 1.1 as measured by the IRC.	Kaplan-Meier estimates (product-limit estimates) will be presented together with a summary of associated statistics (median time, 3-, 6-, 9-, 12-, 24-month rate estimates) including the corresponding two-sided 95% confidence intervals. The confidence intervals for the median will be calculated according to Brookmeyer and Crowley (1982) and confidence intervals for the survival function estimates at above defined timepoints will be derived using the log-log transformation according to Kalbfleisch and Prentice (2011) (conftype=loglog default option in SAS Proc LIFETEST). The estimate of the standard error will be computed using Greenwood's formula.	
PFS will be censored at the date of last progression-free tumor assessment or date of first study treatment, whatever is later.
 
Censoring rules (details provided in body text):
 

- No event (PD or death)

- No baseline and/or post-baseline assessment

- Start of new anticancer treatment

- Event after two or more subsequent missing response assessments

Sensitivity analysis 1 (ITT)			
PFS will be censored at the date of last tumor assessment with outcome CR, PR or SD or date of first study treatment, whatever is later.
 
Censoring rules (details provided in body text):
 

- No event (PD or death)

- No baseline and/or post-baseline assessment

Sensitivity analysis 2 (ITT)	Time from first administration of study treatment until the first documentation of progression of disease (PD) or death due to any cause, whichever occur first, per RECIST 1.1 as measured by the Investigator.	PFS will be censored at the date of last tumor assessment with outcome CR, PR or SD or date of first study treatment, whatever is later.

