		
Censoring rules (details provided in body text):
 
 
- No event (PD or death)
 
- No baseline and/or post-baseline assessment
 
- Start of new anticancer treatment
 
- Event after two or more subsequent missing response assessments
 

Sensitivity Analysis 1: PFS counting all events (PD and death) regardless of the start of a new anticancer therapy and ignoring the number of missing evaluable tumor assessments before progression or death

Sensitivity Analysis 2: PFS as assessed by the Investigator

**Progression-Free Survival (PFS)** time is defined as the time from first administration of study treatment until the first documentation of progression of disease (PD) or death due to any cause, whichever occur first.

PFS = (date of PD or death or censoring – date of first administration of study treatment + 1)/30.4375 (months).

The following censoring rules will also be applied for the PFS computation:

- Participants with no event (PD or death) will be censored on the date of the last adequate tumor assessment
- Participants who do not have a baseline tumor assessment or who do not have any evaluable post-baseline tumor assessments will be censored at the date of first administration of study treatment unless death occurred on or before the time of the second planned tumor assessment (i.e. 16 weeks) in which case the death will be considered an event.
- Participants who start new anticancer treatment prior to an event will be censored on the date of the last evaluable tumor assessment before anticancer therapy is given.

Note: any systemic anticancer therapy, any anticancer surgery and any anticancer radiotherapy with exception of palliative bone radiotherapy will be considered as new/subsequent anticancer therapy and will lead to censoring.

- Participants with an event after two or more subsequent missing response assessments (i.e. no assessments in 112 days during the first 12 months of follow-up or 168 days after the first 12 months of follow-up) will be censored on the date of the last evaluable tumor assessment.

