The last tumor assessment date is defined as the last available and evaluable tumor assessment performed prior to the cut-off date (or prior to end of study, i.e. participants lost to follow-up or who withdraw consent) or prior to subsequent anticancer therapy. If no evaluable tumor assessment is available, this date will be the date of first administration of study treatment.

Censoring rules are also summarized in [Table 5](#).

**Table 5** Censoring Rules for Primary and Sensitivity Analysis of PFS

Situation		Primary Analysis	Sensitivity Analysis 1	Sensitivity Analysis 2
No PD and no death	New anticancer therapy is not initiated	Censored at last tumor assessment*	Censored at last tumor assessment*	Censored at last tumor assessment*
	New anticancer therapy is initiated	Censored at last tumor assessment* before new anticancer therapy	Censored at last tumor assessment*	Censored at last tumor assessment* before new anticancer therapy
No baseline assessment or no evaluable post-baseline assessment	No death or death >16 weeks after start of study treatment	Censored at date of first administration of study treatment	Censored at date of first administration of study treatment	Censored at date of first administration of study treatment
	Death ≤16 weeks after start of study treatment	Progressed at date of death	Progressed at date of death	Progressed at date of death
PD or death	After ≤1 subsequent missing response assessment a	Progressed at date of document PD or death, whichever came first	Progressed at date of documented PD or death, whichever came first	Progressed at date of documented PD or death, whichever came first
	After ≥2 subsequent missing response assessment a	Censored at last tumor assessment* before missing assessments.	Progressed at date of documented PD or death, whichever came first	Censored at last tumor assessment* before missing assessments
	Before started new anticancer therapy	Progressed at date of document PD or death, whichever came first	Progressed at date of documented PD or death, whichever came first	Progressed at date of document PD or death, whichever came first
	After started new anticancer therapy	Censored at last tumor assessment* before new anticancer therapy	Progressed at date of documented PD or death, whichever came first	Censored at last tumor assessment* before new anticancer therapy

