Sensitivity Analysis 1: PFS counting all events (PD and death) regardless of the start of a new anticancer therapy and ignoring the number of missing evaluable tumor assessments before progression or death

Sensitivity Analysis 2: PFS as assessed by the Investigator

\* with outcome CR, PR or SD. If no adequate tumor assessment, censored at date of first administration of study treatment

a No assessments in 112 days during the first 12 months of follow-up or 168 days after the first 12 months of follow-up

PFS according to RECIST 1.1 as measured by the IRC will be described (secondary endpoints).

The analysis of PFS will be performed with a Kaplan-Meier method (product-limit estimates) and a summary of associated statistics will be presented including corresponding two-sided 95% CIs. The CIs for the median will be calculated according to Brookmeyer and Crowley (1982) and CIs for the survival function estimates will be derived using the log-log transformation according to Kalbfleisch and Prentice (1980) (CONFTYPE=loglog default option in SAS PROC LIFETEST). The estimate of standard error will be computed using Greenwood's formula.

Frequency (number and percentage) of participants with and without event and within each event type (PD or death) will be presented as well as the PFS median, min and max. Number of participants at risk, failed and PFS rates with their CI at 6, 12 and 24 months will also be provided. Censoring reasons will also be described. Censoring reasons are as follows:

- Administrative censoring (ongoing in the study without an event)
- No baseline assessment
- No evaluable post-baseline assessment
- Start of new anticancer therapy
- Event after 2 or more missing or non-evaluable post-baseline assessments
- Withdrawal of consent
- Lost to follow-up

Lost to follow-up will include the following participants:

- Lost to follow-up status is collected on the eCRF treatment termination page or eCRF study termination page prior to the analysis cut-off
- Participants with the last alive date > 14 weeks prior to the analysis cut-off date (duration of 14 weeks is based on the assessment schedule of every 3 months for survival follow-up interval + 2-weeks window)

PFS will also be presented graphically with Kaplan-Meier figures.

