#### 14.4.1 Sensitivity analysis for PFS

The two following sensitivity analyses will be conducted:

1. PFS counting all events (PD and death) regardless of the start of a new anticancer therapy and ignoring the number of missing evaluable tumor assessments before progression or death
2. PFS as assessed by the Investigator (described above in Section 14.4)

Those sensitive analyses will be supported with Kaplan-Meir plots. Listing of progression-free survival by the Investigator will also be provided.

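### The SAP's 112/168-day definition of two missed scans equals the gap left by one missed scan, so some progressions after a single miss are censored in PFS, DOR and DRR

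*SAP*

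**What the plan says.** Protocol Table 1 (Section 1.3) schedules tumor imaging "Q8W up to 12 months, then Q12W". Protocol 9.4.1.2.1 censors PFS for "participants with an event after two or more missing tumor assessments"; this is a count, with no day limit.

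SAP 14.4 keeps the count but defines it as "no assessments in 112 days during the first 12 months of follow-up or 168 days after the first 12 months of follow-up". Footnote a of Table 5 repeats the definition and is attached to both rows that classify progression or death by number of missed scans. The first of those rows, "After ≤1 subsequent missing response assessment", counts the progression or death as an event. The second, for two or more misses, censors at the last tumor assessment before the gap. Table 5 applies this to IRC-assessed PFS and to investigator-assessed PFS (Sensitivity Analysis 2).

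SAP 14.5 gives DOR the primary PFS censoring rules. SAP 14.6 defines DRR as the share of all participants with a DOR of at least 6 months, and Protocol 9.4.1.2.1 counts a DOR censored below 6 months as a failure. SAP Section 7 states that the planned analyses are unchanged from the protocol.

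**The concern.** The day limits equal two scan intervals. For a progression seen on a scan, two intervals between the last scan and the progression scan contain only one missed scan. The limit therefore lies on the one-miss gap, with no allowance for visit windows and no statement of whether it means more than, or at least, that many days. A progression that Table 5 calls an event can be censored by that table's own footnote, depending on a day or two of scheduling or on a programming choice.

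The consequences differ by endpoint. Removing progression events tends to lengthen the Kaplan-Meier curves for PFS and DOR. DRR can only fall, because moving the end of response back to an earlier scan can turn a durable response into a failure but never the reverse. Affected participants would be tabulated under "Event after 2 or more missing or non-evaluable post-baseline assessments" although one scan was missed. Missed scans are foreseeable: SAP 7.1 plans a listing of tumor assessments missed because of COVID-19.

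**Working it through.** **Inputs.** Scan interval 56 days to month 12, then 84 days (Protocol Table 1 and 8.1.1). Visit window ±3 days (treatment-phase heading of Protocol Table 1, assumed to apply to scans). Limits 112 and 168 days (SAP 14.4). One month = 30.4375 days (SAP Section 9). DOR = (end date − response date + 1)/30.4375 (SAP 14.5).

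**1. Where the limits come from.** 2 × 56 = 112 and 2 × 84 = 168.

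**2. Gap to a progression scan after m missed scans: (m + 1) × interval.** The window range allows ±3 days on both scans, so ±6 in total.

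| Schedule | Missed | Nominal gap (days) | Range (days) | SAP limit (days) |
|---|---|---|---|---|
| Every 8 weeks | 1 | 112 | 106–118 | 112 |
| Every 8 weeks | 2 | 168 | 162–174 | 112 |
| Every 12 weeks | 1 | 168 | 162–174 | 168 |
| Every 12 weeks | 2 | 252 | 246–258 | 168 |

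**3. Share of one-miss progressions censored.** Take the two offsets as independent and uniform over −3 to +3 days, giving 7 × 7 = 49 pairs. The gap exceeds the limit in 21 pairs (21/49 = 43%) and equals it in 7, so it is at or above the limit in 28 (28/49 = 57%). Two-miss progressions are always censored, as intended.

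**4. First interval.** SAP 14.4 uses the date of first treatment when there is no earlier evaluable scan. From Day 1 to Week 17 (Day 113) with Week 9 missed is 112 days, range 109–115. The shares are 3/7 = 43% and 4/7 = 57%.

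**5. Change of schedule at month 12.** If the 12-weekly grid runs from Week 49 (an assumption), a missed Week 49 scan leaves Day 421 − Day 281 = 140 days between Week 41 and Week 61, range 134–146. That is always censored under 112 days and never under 168. The SAP does not say which limit governs an interval that spans month 12.

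**6. DRR example.** Response at Week 9 (Day 57), last evaluable scan Week 25 (Day 169), Week 33 missed, progression at Week 41 (Day 281). The gap is 281 − 169 = 112 days.
- Progression counted: (281 − 57 + 1)/30.4375 = 7.4 months, a durable response.
- Censored at Week 25: (169 − 57 + 1)/30.4375 = 3.7 months, a failure.

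The second result follows under the at-least reading, or under the more-than reading if the gap is one or more days longer than 112.

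**7. Illustrative counts.** The documents give no missed-scan rate. A simulation of 3,000 trials of 141 participants assumed exponential PFS with median 2 or 4 months, and 5%, 10% or 15% of scans missed independently. One-miss progressions wrongly censored per trial:

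| Events | Limit read as > | Limit read as ≥ |
|---|---|---|
| All progressions | 4.2–11.1 | 5.7–14.9 |
| 30% deaths | 3.0–7.8 | 3.9–10.4 |

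**8. Deaths.** After a scan, two further scans have fallen due by 112 (or 168) days, so apart from the window the limit is about right for deaths. At most 0.2 deaths per trial were wrongly censored.

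**The case against.** The strongest reply is that the estimates hardly move. Under the assumptions of step 7 with all events progressions, mean 6-month PFS rises over a true count rule by 0.0–1.3 percentage points (more-than reading) or 0.1–1.7 (at-least reading), and median PFS shifts by at most about 0.2 month. The 95% confidence half-width for a 39% rate with 141 participants is 1.96 × √(0.39 × 0.61/141), about 8 points. With up to 20% of scans missed and median PFS of 2.5–6 months, the shift is 0.2–2.9 points. DRR status flips only when the last scan before the gap falls 112 or 168 days after first response. Assuming 25 responders (18% of 141), median DOR of 4–12 months and 5–15% missed, that is 0.1–0.5 participants per trial, at most 0.4 points. These endpoints are descriptive; the only test is on ORR. That all stands and limits the size of the problem.

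It can also be said that Table 5 states the count rule, that Sensitivity Analysis 1 restores these events by "ignoring the number of missing evaluable tumor assessments before progression or death", and that the listings allow affected cases to be found. This helps only in part. The SAP presents the day count as the meaning of the count, so programmers will follow it. Sensitivity Analysis 1 also drops censoring for new anticancer therapy, so it does not isolate this effect, and DOR and DRR have no counterpart.

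Read literally, a progression scan exactly on day 112 may not meet the limit. That favors the more-than reading, which still censors 43%. Finally, the simulation omits new-therapy censoring, which would remove some of the counted cases.

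**Conclusion.** The concern holds. The day count in SAP 14.4 and Table 5 footnote a does not implement the two-miss rule for scan-detected progression. It contradicts Protocol 9.4.1.2.1 and Table 5's own one-miss row, and some one-miss progressions are censored under either reading of the limit. The nominal arithmetic needs only the scan schedule. The 43% and 57% shares rest on uniform, independent ±3-day offsets; the 140-day case rests on a 12-weekly grid starting at Week 49; the counts of about 3–15 participants rest on assumed miss rates and PFS medians and are illustrations only.

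The expected effect on 6-month PFS is small, about 0–2 points at 5–15% missed scans, and smaller still on DRR. The primary ORR analysis is unaffected. The rule should still be corrected, because secondary results would otherwise depend on an unstated programming choice and events would be reported under a wrong censoring reason.

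**What to change.** Replace the day count in SAP 14.4 and Table 5 footnote a with a direct count: censor only if two or more consecutive scheduled assessments are missing or non-evaluable between the last evaluable assessment (first dose if there is none) and the documented progression or death. State that the same text governs DOR and therefore DRR, and give the convention for assigning late or unscheduled scans to scheduled slots.

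This restores the protocol rule, serves progression and death alike, and removes the ambiguity at month 12. A longer day limit would be second best. To separate one miss from two for progression it would have to lie at 119–161 days on the 8-week schedule and 175–245 days on the 12-week schedule, and deaths would need a separate limit.

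The cost is one sentence, one footnote and one programming rule with its slot-assignment convention. No new data are needed.

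### PFS Sensitivity Analysis 1 is defined as counting every death whatever the number of missing scans, but its censoring table drops deaths after 16 weeks in participants with no evaluable scan

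*SAP*

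**What the plan says.** **Definition.** SAP 14.4.1 describes Sensitivity Analysis 1 as "PFS counting all events (PD and death) regardless of the start of a new anticancer therapy and ignoring the number of missing evaluable tumor assessments". SAP 14.4 gives the same description in the body text and under Table 5. Protocol 9.4.1.2.1 lists it among the alternative censoring rules as "an analysis which counts death and progression according to RECIST 1.1 as PFS event regardless of the start of a new anticancer therapy", also ignoring the number of missing evaluable assessments. None of these statements carries an exception.

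**No-assessment rule.** A separate sentence in Protocol 9.4.1.2.1 says that participants without a baseline scan or "who do not have any postbaseline tumor assessments will be censored on the date of first administration of study intervention", unless they die by the time of the second planned scan. SAP 14.4 repeats this for PFS generally and puts that time at 16 weeks. Details are left to the SAP.

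**How the SAP applies the rule to Sensitivity Analysis 1.** The 14.4 summary table keeps "No baseline and/or post-baseline assessment" as one of two censoring rules for this analysis. In Table 5 the row "No death or death >16 weeks after start of study treatment", for participants with no baseline or no evaluable post-baseline scan, gives censoring at first administration in all three columns.

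**The row for two or more missed scans.** For progression or death after at least two missing assessments, the Sensitivity Analysis 1 column counts an event. Footnote a defines the condition as "No assessments in 112 days during the first 12 months of follow-up or 168 days after the first 12 months of follow-up".

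**The concern.** A sensitivity analysis that drops the missed-scan rule should show how far the main PFS result depends on that rule. The main analysis sets a participant with no evaluable scan and a death after 16 weeks to zero follow-up, although the death date is known. A reader of the Sensitivity Analysis 1 label would expect that death to be counted. As tabulated it is not, and Sensitivity Analysis 2 (Investigator assessment) keeps every main-analysis rule. So no specified PFS analysis shows what this censoring does.

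There is also a programming risk. If the missed-scan row is taken to reach the same participant, one programmer could count the death and another could censor it at Day 1.

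**Working it through.** **1. The two thresholds coincide.** Scans are 8-weekly in year 1 (Protocol 8.1.1). Two missed scans are 2 × 8 × 7 = 112 days, which reproduces the year 1 figure in footnote a. The no-assessment row turns at 16 × 7 = 112 days. The later figure also reproduces: 2 × 12 × 7 = 168 days.

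**2. A test case.** Take a baseline scan, no evaluable post-baseline scan, and death on Day 140.

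| Source | Treatment under Sensitivity Analysis 1 |
|---|---|
| Definition (14.4, 14.4.1; Protocol 9.4.1.2.1) | Event on Day 140 |
| Table 5, no-assessment row, death after 16 weeks | Censored at first dose |
| 14.4 summary table | No-assessment rule kept, so censored |
| Table 5, row for two or more missed scans, if it applies | Event on Day 140 |

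The first line conflicts with the second and third whatever is decided about the fourth. In the other two columns both Table 5 rows lead to first administration, so any overlap there does no harm.

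**3. Size.** The documents give neither the number of such deaths nor an expected PFS. Assumptions: m = 1 to 11 such deaths among 141; everyone else has exponential time to progression with median M = 2 to 4 months, detected only at scheduled scans; 1 month = 30.4375 days (SAP 9).

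Let S(t) be the PFS rate in the other participants, which is the tabulated result because participants censored on Day 1 drop out. Let Sd(t) be the share of the m participants still alive at t. Then

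defined minus tabulated = (m/141) × [Sd(t) − S(t)].

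*3 months (91.3 days).* All affected deaths fall after Day 112, so Sd = 1 and the sign is fixed. The only scheduled scan before 3 months is near Day 57, and 57/30.4375 = 1.873 months.

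- M = 2: S = 2^(−1.873/2) = 0.523. For m = 11: (11/141) × 0.477 = **+3.7 points**.
- M = 4: S = 2^(−1.873/4) = 0.723. For m = 1: (1/141) × 0.277 = **+0.2 points**.

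*6 months (182.6 days).* The last scheduled scan before this is near Day 169, or 5.552 months, so S = 0.146 (M = 2) to 0.382 (M = 4).

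| Timing of the affected deaths | Sd | Smallest change | Largest change |
|---|---|---|---|
| All before 6 months | 0 | −0.1 (M = 2, m = 1) | −3.0 (M = 4, m = 11) |
| Uniform over Days 113–400 | 0.757 | +0.3 (M = 4, m = 1) | +4.8 (M = 2, m = 11) |

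The sign turns positive once the share of these deaths falling after 6 months exceeds S, which is 14.6% (M = 2) to 38.2% (M = 4).

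A Kaplan-Meier simulation with 8-weekly scans and administrative censoring gave +0.19 to +3.71 points at 3 months, and −0.11 to −2.99 or +0.27 to +4.74 at 6 months under the same two timings.

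**The case against.** The strongest reply is that the rule is deliberate. The definition names two relaxations, new therapy and the number of missing scans. The summary table drops exactly those two rules for Sensitivity Analysis 1 and keeps the no-assessment rule, and Table 5 agrees with it. The protocol states the no-assessment rule separately and defers details to the SAP. This may well be the intention, and it stands as a reason to offer a second form of fix. It does not remove the mismatch: the label promises all deaths and the exception appears nowhere in it.

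A reader might go further and conclude that the column certainly gives two answers for one death. The documents do not support that as a certainty.

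- **Against overlap.** In the other columns the missed-scan row censors at the last scan before the missing ones, which suggests an earlier scan exists. SAP 14.4 lists absence of an evaluable post-baseline scan as its own censoring reason, apart from "Event after 2 or more missing or non-evaluable post-baseline assessments". Letting the specific row govern also gives every cell a use.
- **For overlap.** Footnote a requires no prior scan. The asterisk note attached to that row elsewhere provides that "If no adequate tumor assessment, censored at date of first administration of study treatment", although the same note also serves rows that need this fallback anyway.

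Overlap is therefore a plausible reading. What can be said firmly is that no precedence is stated.

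A reader might also infer a 3-month effect of up to 5 points. That comes from a smooth exponential curve: for M = 2 and m = 11, (11/141) × (1 − 2^(−3/2)) = 5.0. It ignores the 8-weekly scans. With them the maximum is about 3.7, and eleven such deaths is itself an assumption. The 14.4 summary table lists a 3-month PFS rate, but the later 14.4 text lists only 6, 12 and 24 months.

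**Conclusion.** The point holds as a mismatch between the definition of Sensitivity Analysis 1 and the rules tabulated for it, with an unstated precedence between two Table 5 rows. Followed as written, the table produces an analysis that does not match its label.

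The impact is minor. Under the stated assumptions the 3-month rate changes by about +0.2 to +3.7 points, the 6-month rate moves in either direction with the timing of the deaths, and a single such death is negligible. These figures are the gap between the tabulated and the defined analysis. They should not be read as a bias against true PFS.

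This is a descriptive sensitivity analysis of a secondary endpoint, with no test or decision rule. The primary ORR test is unaffected and OS still counts these deaths. The branch for no baseline scan should be nearly empty, because IRC-verified measurable disease is an entry criterion. The planned listings of event and censoring reasons would let affected participants be found.

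**What to change.** If Sensitivity Analysis 1 is meant as defined:

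1. In its Table 5 column, for no baseline or no evaluable post-baseline scan, count death at any time as an event on the date of death. Censor at first administration only if there is no death.
2. State how a progression recorded without a baseline scan is handled.
3. Align the Sensitivity Analysis 1 entry in the 14.4 summary table.
4. In the 14.4 body text, limit the 16-week rule to the main analysis and Sensitivity Analysis 2, and leave those two columns unchanged.

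If the exception is intended, add one clause to the definition wherever it appears, and one note to Table 5 that the no-assessment row takes precedence over the row for two or more missed scans.

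Either way the cost is a few short text edits and no new data.
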